5. STATISTICAL CONSIDERATIONS

- 5.1. *Study Design.* The clinical trial is a two-arm randomized controlled trial. After completion of the intervention, data analysis will be conducted according to the statistical analysis plan outlined below. Descriptive statistics will be performed prior to conducting the statistical analyses. An intention-to-treat (ITT) analysis of the results will be based on the initial assignment of the randomized participants. With the ITT approach, participants will be analyzed according to the treatment assignment, even if the participant drops out of the study. The ITT approach minimizes biased comparisons among the treatment arms. Missing data will be imputed using the last collected data from the subject prior to dropout.
- 5.2. *Accrual.* It is estimated that 18-months will be necessary to enroll the targeted sample size. Accrual will be reported by race, ethnicity, gender, and age.
- 5.3. *Study Duration.* Survey results and wearable data will be actively collected from participants over the course of 12 weeks. At the conclusion of the 12 weeks, passive collection of wearable data through the app will continue for up to one year for each participant who opts-in to continue using the app. Medical records may be accessed for up to five years after the conclusion of the 12-week collection period.
- 5.4. *Randomization.* Blocked randomization will be used to limit bias and achieve an equal distribution of participants to the intervention and control arms of the study (69 randomized, 69; with 23 from each cancer population in each arm). This approach will recruit participants in small blocks to ensure that half of the participants within each block will be allocated to the treatment and the other half to the control. The size of the blocks will be permuted to limit selection bias, and within each block, the order of patients will be random. The study statistician will create a randomization list before the study begins enrollment using the statistical package R. This list will be used by the study group in assigning patients to the correct study arm.
- 5.5. *Blinding.* Study arm assignments cannot be blinded to the investigators or the rest of the study team because it will be known whether participants have SYNC on their mobile device or not (due to technical purposes).
- 5.6. *Primary Endpoint.* The primary objective of the study is to test the effects of SYNC in a randomized controlled clinical trial design. Patients will be randomly assigned to the treatment arm or the control arm. The primary objective is to quantify the effects of the light interventions delivered by SYNC on patient fatigue.
- 5.7. *Sample Size Considerations.* We will enroll 138 cancer patients, with half in the intervention arm and half in the control arm. Our primary endpoint is the PROMIS 4-item Fatigue Short Form. The age- and sex-adjusted norm for the Fatigue scale is 50 points, with a standard deviation of 10 points. These statistics have been shown to be largely generalizable to the cancer patient population (mean: 52, standard deviation 7.6). Our study will have power of 0.80, assuming a two-sided Type I error rate of 0.05, to detect an effect size of half the standard deviation between the intervention and control arms if 64 cancer patients are enrolled in each of the control and intervention groups. A mean difference of one-half a standard deviation is clinically meaningful and is considered a medium effect size for clinical trials. During the primary analysis, we will adjust for the fact

that there are three cancer populations in our data and will look for a well-defined effect that is marginal within each population. We will accrue a total of 69 patients in each arm to account for attrition of data, assuming a 7% dropout rate from the trial.

5.8. PROMIS® measures use Item Response Theory (IRT), a family of statistical models that link individual questions to a presumed underlying trait or concept of global health represented by all items in the scale. PROMIS® instruments are scored using item-level calibrations. The most accurate way to score a PROMIS® instrument is to use the Health Measures Scoring Service, which our Study Team has experience with. This method of scoring uses “response pattern scoring,” which uses responses to each item for each participant. Response pattern scoring is especially useful when there is missing data (i.e., a respondent skipped an item), or different groups of participants responded to different items).

There are four key features of the score for PROMIS® Fatigue:

1. Reliability: The degree to which a measure is free of error. It can be estimated by the internal consistency of the responses to the measure, or by correlating total scores on the measure from two time points when there has been no true change in what is being measured (for z-scores, reliability = $1 - SE^2$).
2. Precision: The consistency of the estimated score (reciprocal of error variance).
3. Information: The precision of an item or multiple items at different levels of the underlying continuum (for z-scores, information = $1/SE^2$).
4. Standard Error (SE): The possible range of the actual final score based upon the scaled T-score. For example, with a T-score of 52 and a SE of 2, the 95% confidence interval around the actual final score ranges from 48.1 to 55.9 ($T\text{-score} \pm (1.96 \times SE) = 52 \pm (1.96 \times 2) = 48.1 \text{ to } 55.9$)

The final score is represented by the T-score, a standardized score with a mean of 50 and a standard deviation of 10 points.

5.9. *Interim Analysis*. There will be no interim analyses for efficacy or futility for this trial.

5.10. *Patient Characteristics*. Patient characteristics will be summarized for all participants. Patient characteristics to be examined may include: age, gender, race/ethnicity, treatment and pathology information (including dates), and clinical outcomes; e.g. survival, relapse, and toxicities.

5.11. *Analysis Populations and General Analysis Guidelines*.

5.11.1. Primary Analysis Population. All participants enrolled, consented, and completing at least the baseline outcome measures will be included in the primary analysis population. Analyses for the primary and secondary endpoints will use the primary analysis population: The primary analysis will occur once all patients have been followed for the duration of the 12-week trial, data adjudication completed, and data are locked.

5.11.2. General Analysis Guidelines. Primary analyses for the primary, secondary, and exploratory endpoints will use the primary analysis population. Analyses of each endpoint in each population will follow the

analysis plans, as described below. We expect minimal missing data (<5%) for the primary endpoint and secondary endpoints based on past experience with mobile app studies.

5.12. *Analysis of Primary Endpoint.* Analysis will be an intent-to-treat analysis that includes all participants. Mean Global Health scores at the end of the trial will be compared using a two-sample *t*-test (or Wilcoxon Rank Sum test if non-normality is apparent) with a significance level of 0.05. Linear regression models will be performed to complement the results of the *t*-test and adjust for specific baseline participant's characteristics (e.g., demographic, social, environmental) to increase the precision of our inference. There is a possibility that patient characteristics will be unbalanced since our randomization scheme will be applied to participants. Thus, our models also will assess potential moderating or mediating effects.

5.13. *Analysis of Secondary Endpoint.*

Mean PROMIS scores (PROMIS sleep disturbances, anxiety, depression, physical function, and global health) for each arm at the end of the trial will be compared using a two-sample *t*-test (or Wilcoxon Rank Sum test if non-normality is apparent) with a significance level of 0.05. Linear regression models will be performed to complement the results of the *t*-test and adjust for specific baseline participant's characteristics (e.g., demographic, social, environmental) to increase the precision of our inference. There is a possibility that patient characteristics will be unbalanced since our randomization scheme will be applied to participants. Thus, our models also will assess potential moderating or mediating effects.

5.14. *Analysis of Exploratory Endpoints.*

5.14.1. Patient activity. The accelerometer data of each subject will be transformed into a low-dimensional representation using motif discovery algorithms.⁷⁹ Such techniques are completely data-driven, and search for motifs (i.e., patterns) in the data that occur more often than chance. A signal can then be represented by the number of times a particular motif occurs. Others have successfully used such techniques for representing a variety of waveform data, including accelerometer and continuous glucose data.⁸⁰⁻⁸² The accelerometer data will be processed to derive estimates of total sleep duration (i.e., hours per night), wake after sleep onset, and sleep efficiency (i.e., ratio of sleep to wake). The variables will be compared between arms.

5.14.2. Patient health care utilization. The total count of hospital days, ED visits, readmissions, and ambulatory care clinic visits during the trial, with adjustment for follow-up, will be compared between arms using a Poisson regression model, with adjustment for potential mediating or moderating effects of patient characteristics, if needed. The data will be captured at the time of PRO assessments.

5.14.3. Patient sleep aid utilization. The total number of sleep aids being used by the patients, as well as the types, will be collected via weekly surveys over the course of the trial.

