Accrual Objective: We will enroll 138 cancer patients, with half in the intervention arm and half in the control arm. Our primary endpoint is the PROMIS 4-item Fatigue Short Form. The age- and sex-adjusted norm for the Fatigue scale is 50 points, with a standard deviation of 10 points. These statistics have been shown to be largely generalizable to the cancer patient population (mean: 52, standard deviation 7.6). Our study will have power of 0.80, assuming a two-sided Type I error rate of 0.05, to detect an effect size of half the standard deviation between the intervention and control arms if 64 cancer patients are enrolled in each of the control and intervention groups. A mean difference of one-half a standard deviation is clinically meaningful and is considered a medium effect size for clinical trials. During the primary analysis, we will adjust for the fact that there are three cancer populations in our data and will look for a well-defined effect that is marginal within each population. We will accrue a total of 69 patients in each arm to account for attrition of data, assuming a 7% dropout rate from the trial.

Accrual Period: The estimated accrual period is 1.5 years

Study Duration: Data will be collected from participants for 12 weeks. Passive collection of wearable data through the app will continue for up to one year for each participant who opts-in to continue using the app, and medical records may be accessed for up to five years after the conclusion of the 12-week collection period.

STUDY SCHEMA: SCHEDULE OF EVENTS

[figure not shown]

Diagram outlining the survey data collected over the trial. Note: "Control actions" here refers to following "dummy" lighting recommendations that are minimally expected to affect the circadian clock.

TIME AND EVENTS TABLE

Patient Events Timeline			
Every day after starting the trial:	Every week, starting on the first day of the trial:	On the first day and last day of the trial:	At any point in time:
Single question daily fatigue survey	PROMIS Fatigue survey, "How is your experience with the app?" questionnaire, sleep aid usage survey	PROMIS Sleep, Anxiety, Depression, Physical Function, Global Health	App experience free response

Study Timeline	Year 1				Year 2			
	Q1	Q2	Q3	Q4	Q1	Q2	Q3	Q4
Revise the app to include the capacity to collect survey responses	X	X						
Begin identifying potential subjects using UofM Health Research website		X						

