1. STUDY DESIGN

- 1.1. *Study Overview.* This study will use a two-arm randomized study design. Participants will be recruited across three cancer types. Each of the participants will be randomized to an active “intervention” arm (using the full SYNC app) or to a control arm (using a “dummy” version of the SYNC app that gives recommendations for light at times that should not significantly affect the circadian clock). The random allocation of participants to the treatment arm or control arm establishes the basis for testing the statistical significance or difference between the groups in the measured outcome (patient fatigue, assessed by a daily 1-question fatigue survey and the PROMIS 4-item Fatigue). Patient age, gender, and other prognostic baseline characteristics that could potentially confound an observed association, including those that are unknown or unmeasured, will be distributed equally, except through chance alone, through random assignment. Thus, this design is well-suited to our goal of assessing the efficacy of a mobile health intervention, SYNC, on participants.
- 1.2. *Primary Hypothesis.* The primary hypothesis is that a mobile-app delivered circadian intervention (SYNC) will reduce patient fatigue.
- 1.3. *Study Objectives*
 - 1.3.1. Primary Objective. To test the difference between the “intervention” (full SYNC app) arm and the control (limited SYNC app) arm in the measured outcome of patient fatigue, assessed by daily 1 question surveys and weekly 4-item PROMIS questionnaires over the course of 12 weeks.
 - 1.3.2. Secondary Objective. To determine the change in sleep disturbances, anxiety, depression, physical functioning, and global health through PROMIS questionnaires, between baseline and the 12-week assessment in both the control and intervention arms, and to look for differences in this change between the two arms.
 - 1.3.3. Exploratory Objectives
 - 1.3.3.1. Change in patient physical activity through physiological data capture using the wearable sensors in the control versus intervention arm.
 - 1.3.3.2. Change in patient health care utilization (e.g., total count of hospital days, readmissions, and ambulatory care clinic visits) in the control versus intervention arm
 - 1.3.3.3. Change in patient sleep aid usage in the control versus intervention arm.
- 1.4. *Participant Eligibility*
 - 1.4.1. Inclusion Criteria

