- 1.5.4. Participants will be allowed to use sleep aids over the course of the trial. There will be no restriction on their usage; however, subjects will be asked to report on a weekly basis what sleep aids they consumed, as well as the number of alcoholic drinks they consumed. This survey will be carried out in the app.
- 1.5.5. Once the trial has begun, study coordinators will track completion of surveys, and in the event of missing data will follow-up with subjects to assess challenges to encourage survey completion. SYNC software will be maintained in collaboration with Arcascope, Inc. After randomization, subjects will complete baseline assessments, as outlined in the metrics Appendix. They will be asked to wear the wearable device day and night for twelve weeks. During this time, the app will deliver ecological momentary assessments of fatigue daily at random times of day and the validated 4-item PROMIS Fatigue questionnaire weekly to both the control and interventional groups. At the end of the twelve-week period, the subjects will remotely complete end-of-trial assessments.
- 1.5.6. Intervention arm (SYNC app): Participants randomized to the intervention arm will be instructed on how to download the app on their mobile phones (iOS) and how to operate the wearable device. The app will record when the user opens the app, as well as when they check off having completed an assigned task; e.g. “getting bright light exposure”. Please see **Appendix A** to view the components of the wearable device. Please see **Appendix B** to view specifications of the mobile app. Any PHI information will be stored on University of Michigan servers in a secure way. Only non-PHI information will be stored and collected via the Sync app. The SYNC will be downloaded onto patient mobile phones and can be used freely throughout the intervention period because it contains no PHI data.
- 1.5.7. Control arm: Participants randomized to the control arm will be instructed on how to download the SYNC app and how to operate the wearable sensor. Their research ID will trigger the “control” recommendations from SYNC, which are chosen to minimize circadian effect. Any PHI information will be stored on University of Michigan servers in a secure way. Only non-PHI information will be stored and collected via the Sync app. The SYNC will be downloaded onto patient mobile phones and can be used freely throughout the intervention period because it contains no PHI data.

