- 4.4. *Post-Intervention Evaluation*: PROMIS Patient-Reported Outcomes (PROs) – Well-being or HRQOL assessments will be completed at 12 weeks, post-intervention. This survey must be completed within two weeks after the 12-week intervention period. The surveys will be obtained directly through the SYNC app on mobile phones. Based on prior work, our Study Team has experience administering PROMIS PROs on mobile devices.
- 4.5. *Participant Withdrawal*: At any time, a participant may request that her or his data no longer be collected. The participant may make this request to the Research Coordinator or to any member of the Study Team. A note will be made in the patient chart documenting the reason the patient withdrew from the study. Participants may also be removed for the following reasons: development of disease recurrence or progression, in the event that the IRB or sponsor decides to close the study, or if the treating physician thinks it is no longer in the best interest of the patient.
- 4.6. *Study Regulations*: The trial will be performed in accordance with all applicable regulatory requirements and laws.
- 4.7. *Risks*.

4.7.1. Wearable Sensor Device: Patient Subjects who agree to wear the device(s) for data collection may experience mild skin irritation, which will be monitored by the care team. The subject can decline to wear the device(s) or request to try a different device(s) that may be more comfortable. Subjects who decline to wear the wearable device will be replaced and not included in the statistical analysis. All subjects will be instructed to remove the device before any scans or radiation therapy.

4.7.2. Confidentiality: There is a possible risk of loss of confidentiality. However, every effort will be made to keep your medical information confidential. We will code data by assigning a number to each individual patient and then store the data by that number. No mention of patient subject identities is made in analyses of the data or in any publications, which result from such research.

4.8. **Adverse Event Reporting Requirements.**

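### Last observation carried forward sets a dropout's change to zero on the five first-day/last-day PROMIS scales, with no sensitivity analysis planned; the expected harm is modest and the repair is cheap

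*Combined protocol and SAP*

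**What the plan says.** - **Rule.** Section 5.1, within the intention-to-treat paragraph: "Missing data will be imputed using the last collected data from the subject prior to dropout". This is a single carried-forward value (LOCF).
- **Who is analysed.** Section 5.11.1: "All participants enrolled, consented, and completing at least the baseline outcome measures will be included in the primary analysis population".
- **Schedule.** The Time and Events Table places "PROMIS Sleep, Anxiety, Depression, Physical Function, Global Health" on the first and last day only. By contrast, section 1.5.5 of the Study Design has the app deliver "the validated 4-item PROMIS Fatigue questionnaire weekly to both the control and interventional groups".
- **Question asked.** The secondary objective (1.3.2) is change "between baseline and the 12-week assessment in both the control and intervention arms", compared by arm. The tests in 5.12 and 5.13 compare end-of-trial means.
- **Expected loss.** Section 5.11.2: "We expect minimal missing data (<5%) for the primary endpoint and secondary endpoints based on past experience with mobile app studies". Section 5.7 assumes 7% dropout. The two figures are not reconciled.
- **Reasons for leaving.** Section 4.5: "Participants may also be removed for the following reasons: development of disease recurrence or progression". It adds: "A note will be made in the patient chart documenting the reason the patient withdrew from the study". Section 4.10 has retention and data completeness reviewed every six months.
- **Related provisions.** Response-pattern scoring (5.8) deals with skipped items inside a form. Coordinators chase missing surveys (1.5.5). The exit survey has a two-week window (4.4). Section 4.7.1 replaces people who decline the wearable and leaves them out of the analysis.

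**The concern.** For the five scales there is no score between day 1 and the last day, so the value carried forward for a dropout is the baseline. The t-test then treats that baseline as an observed week-12 result. The change, which is what the secondary objective asks about, is zero by construction and says nothing about week 12.

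Three things are at stake:
- A true effect may be diluted.
- The difference may be shifted if the arms lose people at different rates while scores are moving.
- No planned analysis would show whether a finding rests on the frozen-score assumption. Withdrawal reasons are recorded, and removal for recurrence or progression may be related to outcome, but no analysis uses that information.

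The plan says intention-to-treat but does not say which effect it wants for people who stop, so the rule cannot be judged against a stated target. The rule is also tied to dropout: a survey missed by someone still in the trial has no stated rule.

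**Working it through.** **Inputs from the plan (5.7, 5.11.2).** Two-sided alpha 0.05; power 0.80; effect 0.5 SD; SD 10 (norm) or 7.6 (cancer population); 64 per arm, raised to 69 for 7% dropout; under 5% missing data expected.

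**Assumed here.** Five points (half of SD 10) is used for the five scales as an illustration, because 5.7 states it only for Fatigue. Baseline to week-12 correlation is 0.6. Dropout is unrelated to outcome. Lower scores are better (signs reverse for Physical Function and Global Health). The 5% is the upper limit of expected missing data, used here as a dropout rate.

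**Step 1: the plan's own figure.** The exact two-sample t-test at 0.5 SD needs 63.77, so 64 per arm, with power 0.801. Then 64/0.93 = 68.8, so 69. Both reproduce. With 69 per arm and no loss, power is 0.830.

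**Step 2: LOCF on a first-day/last-day scale.** Let e be the effect, d the drift common to both arms, and pI and pC the dropout proportions in the intervention and control arms. If dropouts would have kept the effect:

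- intervention mean change = (1 − pI)(d + e)
- control mean change = (1 − pC)d
- LOCF difference = e − pI(d + e) + pC·d

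**Step 3: equal dropout p.** Drift cancels and the difference is e(1 − p).

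| Dropout per arm | e = 5, SD 10 | e = 3.8, SD 7.6 | t-test power, 69 per arm, SD unchanged |
|---|---|---|---|
| 5% | 5 × 0.95 = 4.75 | 3.61 | 0.791 |
| 7% | 5 × 0.93 = 4.65 | 3.53 | 0.774 |

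Simulation gave 4.754 and 4.653. Multiple imputation under missing at random, approximated by maximum likelihood, targets 5.0, with power 0.82 at 5% and 0.81 at 7%.

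**Step 4: dropouts lose all benefit.** The treatment-policy difference at 7% in each arm is itself 5 × 0.93 = 4.65. LOCF matches it; missing at random gives 5.0 and is too large. Worsening imputed intervention-arm scores by 5 points restores it: −5.0 + 0.07 × 5 = −4.65.

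**Step 5: drift with unequal dropout (both assumed).** Take d = −5 and e = −5.

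- 12% intervention, 2% control: −5 + 0.12 × 10 − 0.02 × 5 = −3.9; simulated power 0.60.
- 2% intervention, 12% control: −5 + 0.02 × 10 − 0.12 × 5 = −5.4; simulated power 0.88.
- 7% intervention, 3% control: −5 + 0.7 − 0.15 = −4.45; simulated power about 0.72.
- No true effect, 12%/2%: 0.6 − 0.1 = +0.5; simulated type I error 5.9%.
- No true effect, 7%/3%: 0.35 − 0.15 = +0.2; simulated type I error 5.1%.

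**Step 6: weekly Fatigue 4a.** Assume scores at weeks 0 to 12, a linear course, and a last observed week spread evenly over 0 to 11. The mean last week is 5.5, so a dropout retains 5.5/12 = 46% of the effect and loses about 2.71 of 5 points. The difference becomes −5 + 0.05 × 2.71 = −4.86 at 5% and −5 + 0.07 × 2.71 = −4.81 at 7%. Simulated power is 0.81 and 0.80, about as planned.

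**The case against.** The strongest reply is that little is lost. The endpoint powered in 5.7 is weekly Fatigue 4a, which keeps its planned power. The visible dilution falls on secondary scales for which the plan claims no power. Coordinator follow-up and the two-week exit window should limit missing last-day scores. Missing at random is no safer in itself: step 4 shows it can be further off than LOCF. All of this stands, and it sets the size of the point. It does not answer the absence of any sensitivity analysis or of a stated effect for people who stop.

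A reader might infer more than the documents support:

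- **That LOCF governs all missing data.** It does not. Section 5.8 handles skipped items, missed surveys without dropout have no rule, and 4.7.1 removes those who decline the wearable rather than carrying their scores forward.
- **That LOCF undermines the primary result.** On Fatigue 4a it does not. It would reach the primary test only if 5.12, which names Global Health, were followed literally instead of 5.7.
- **That type I error is inflated, or power falls to 0.60.** Those figures need a 5-point drift and 12%/2% dropout, and the documents give neither. With no drift or equal dropout, and dropout unrelated to outcome, there is no bias under the null.
- **That LOCF is at least conservative.** Step 5 shows it can also enlarge the difference.

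**Conclusion.** The point holds as a cheap improvement of minor to moderate severity. At the plan's own rates, the loss on the five scales is 0.25 to 0.35 points of an illustrative 5, and about 1 to 3 percentage points of power below 0.80. That rests on equal dropout, retained benefit and an SD held at 10. If dropouts lose the benefit, there is no loss against the treatment-policy value. The direction under unequal dropout cannot be settled from the documents, which give no drift and no dropout by arm. The firmer finding is that the plan neither says which effect it wants for people who stop nor provides a way to see how far a result depends on frozen baseline scores.

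**What to change.** 1. In 5.1, state the effect of interest for participants who stop.
2. For the five first-day/last-day scales, make multiple imputation the main method, using arm, the scale's baseline, cancer population and weekly Fatigue 4a scores. Pool the planned t-test and regression comparison by Rubin's rules. Report LOCF as a sensitivity analysis. Keep the Wilcoxon test as a check on observed scores, since Rubin's rules do not pool it directly.
3. For Fatigue 4a, fit a repeated-measures mixed model to all weekly scores with baseline Fatigue and cancer population, or keep the planned test and report that model as a sensitivity analysis. First confirm whether a week-12 Fatigue score exists: the Time and Events Table starts the weekly survey on day 1 and does not list it in the last-day battery. With 12 post-baseline scores an unstructured covariance has 12 × 13/2 = 78 parameters; with 11 it has 11 × 12/2 = 66. Prespecify the structure and a fallback to match.
4. Add a delta-adjusted analysis that makes dropouts' imputed scores worse, for example by 0 to 5 points (an assumed range), in both arms and in the intervention arm only. Worse means higher for Fatigue, Sleep Disturbance, Anxiety and Depression, and lower for Physical Function and Global Health. Report dropout and withdrawal reasons by arm.
5. Do not simply delete the 5.1 sentence. Keep or write a rule for the daily fatigue survey, intermittent missed surveys and the exploratory endpoints.
6. Reconcile 5.12 (Global Health) with 5.7 (Fatigue 4a), and the 4.7.1 exclusion with the intention-to-treat wording in 5.1, 5.11.1 and 5.12.

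**Cost.** SAP wording and some programming; no extra patients, visits or surveys. The downside is reliance on missing at random, which gives −5.0 against a true −4.65 if dropouts lose the benefit at 7% dropout. Item 4 is therefore a required part of the change. No power gain is claimed for the mixed model.
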